#### 4.659 Adverse Event Relationships

The Investigators will evaluate whether or not the adverse events were related to the procedure, study requirements, and/or investigational products (e.g., JS device, angioplasty balloon, drug coating) according to the following categories:

**Related:** AE that has a strong temporal relationship to the study procedure, a study requirement, or the presence or performance of the investigational device/system or drug and an alternative etiology is highly unlikely.

**Possibly Related:** AE that has a temporal relationship to the study procedure, a study requirement, or the presence or performance of the investigational device/system or drug and an alternative etiology is unlikely.

**Not Related:** AE is due to the underlying disease state or concomitant medication or therapy, and was not caused by the study procedure, a study requirement, or the investigational device/system or drug.

**Not Assessable:** It is not possible to assess whether or not the adverse event is related to the study procedure, a study requirement, or the investigational device/system or drug.

#### **4.660 DEATHS**

Each subject death must be reported to the Sponsor. A death must be reported to the Sponsor or representative as soon as possible (within 24 hours) after the site's knowledge of the event. A written report will be provided to the Sponsor within 10 business days after the Investigator learns of a death and will be provided to the EC according to reporting guidelines. It is requested that a copy of the death certificate, autopsy report, and any other source documents related to the death be sent to the Sponsor or representative when available. In the event that no source documents are available, the PI will be required to submit a letter to the Sponsor describing the circumstances of the subject's death.

#### 4.661 CORE LABORATORY REQUIREMENTS

#### 4.662 ANGIOGRAPHIC CORE LABORATORY

An independent Angiographic Core Laboratory will review all scheduled and unscheduled angiographic procedure data. See Core Lab Angiographic Protocol.

#### 4.663 ULTRASOUND CORE LABORATORY

An independent Ultrasound Core Laboratory will review all scheduled and unscheduled duplex scans and intravascular ultrasounds. See Core Lab Duplex Ultrasound Protocol.

#### 4.664 CLINICAL EVENTS COMMITTEE

An independent Clinical Events Committee (CEC) will be established. The CEC will consist of physicians who are not Investigators in the study and who do not have any significant investment in Boston Scientific, Bard or any of their entities. The committee may include, but not be limited to, the specialties of interventional cardiology, vascular surgery, and interventional radiology.

The CEC is responsible for reviewing all reported adverse events. The CEC will classify the pertinent outcome events as defined in the Study Protocol.

#### 4.665 DATA SAFETY MONITORING BOARD

An independent Data Safety Monitoring Board (DSMB) will be established. The DSMB will consist of a biostatistician and physicians from a variety of relevant medical specialties, including interventional cardiology, vascular surgery, and interventional radiology, who are not Investigators in the study. Members will not have any significant investment in Boston Scientific or Bard, or any of their entities.

The role of the DSMB will be to monitor and make recommendations regarding the protocol and the overall conduct of the study, to ensure the rights, safety, and welfare of the study participants, and to evaluate interim data to determine if there are any specific safety concerns.

The DSMB will convene when 30-day safety data are available for 100 randomized subjects. Subsequently, the DSMB will review the data at time intervals per their discretion.

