	Safety: Major Adverse Events (MAE) at 30 days : unplanned amputation, total mortality or TLR at 30 days (TLR includes bail out stenting)		
DSMB	The study will be evaluated for safety after the first 60 patients enrolled. Stopping rule will be based on freedom from MAE at 30 days that is $> 78\%$ (bailout stent in the PTA control arm ranged from 7 to 20% in the randomized trial. Bailout stent is included as a MAE (part of the TLR definition). If maximum bailout stent occurs (20%), this allows a 2% amputation/death rate within 1 month before the study is stopped i.e. total events of 22%, or freedom from events of 78%).		
Secondary endpoints	1. Device Outcome: Categorized by < 50% residual stenosis following JS atherectomy alone and without additional adjunctive PTA or bail out procedures as determined by the Angiographic Core Laboratory.		
	2. Procedural Outcome: Categorized by < 30% residual stenosis following the protocol-defined treatment (JS + PTA) with provisional or bail out procedures as determined by the Angiographic Core Laboratory.		
	3. Procedural Success: Defined as $\leq 30\%$ residual diameter stenosis following JS + PTA without provisional or bailout procedures.		
	4. Target Lesion Revascularization (TLR) at 6 months (with no bailout stent included): TLR is defined as retreatment of the index lesion (extended 1 cm proximal and distal to the lesion) at 6 months. Intra-procedural bail out stenting of the index lesion is NOT considered meeting a TLR endpoint. (ITT analysis)		
	5. Target Lesion Revascularization (TLR) at 1 year: TLR is defined as retreatment of the index lesion (extended 1 cm proximal and distal to the lesion) at 1 year		
	ITT (bail out stent in the Lab is considered as TLR) ITT (bail out stent in the Lab is not considered as TLR)		
	
 
6. Target Lesion Patency at 6 months and 1 year: Defined as PSVR ≤ 2.5 at the treated site or < 50% stenosis by angiography as determined by the Angiographic Core Laboratory in the absence of TLR, amputation, and/or surgical bypass (the evaluation of patency is extended to one cm proximal and one cm distal to the target lesion)
 
		
	7. Clinically Driven Target Lesion Revascularization at 6 months and 1 year: Defined as any re-intervention or artery bypass graft surgery involving the target lesion in which the subject has a ≥ 70% diameter stenosis (Peak Systolic Velocity Ratio (PSVR) > 3.5 or on		

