#### **DURATION OF THE STUDY**

The estimated duration of the study is approximately two years from the time of first subject enrollment to the last Study Protocol required follow-up visit. Subjects will be followed for 6 months for the primary endpoint and 1 year for the secondary endpoints.

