### **4.0 METHODOLOGY**

#### 4.1 STUDY DESIGN

This is a prospective, multicenter (up to 14 sites), single arm study. Patients will be treated with plaque excision using JetStream XC (JS) followed by adjunctive balloon angioplasty (PTA). Each subject must meet all inclusion criteria and no exclusion criteria. A subject will be enrolled in the study only after angiography and confirmation of ISR in the FP segment. All subjects will be followed up to 6 months after enrolment for the primary endpoint and 1 year for several secondary endpoints.

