### Safety

**Major Adverse Events (MAE) at 30 days**: unplanned amputation, total mortality or TLR at 30 days (TLR includes bail out stenting)

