#### 6.4 **RISK MITIGATION**

The CEC committee will adjudicate every adverse events and unexpected device related events. DSMB will meet at completion of the first 30 patients and at 60 patients to analyze procedural and follow up events. Recommendations will be made to continue or stop the study based on these 2 interim analysis. All investigators will have to prove experience with at least 10 Jetstream cases with no significant events. Also, investigators will be trained on the protocol to ensure adherence to the inclusion and exclusion criteria and for timely reporting of adverse events as recommended by the IRB and FDA. Subjects will learn about the protocol from investigators and designated coordinators. Voluntary participation will be emphasized. Patients will sign informed consent form (see Appendix C for the ICF).

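### Section 4.665 has the DSMB convene on 30-day data from 100 randomized subjects, which conflicts with the 60-patient stopping-rule look in the synopsis and the 30- and 60-patient looks in section 6.4 of a single-arm study

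*Combined protocol and SAP*

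**What the plan says.** Three places set the timing of DSMB review.

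- **Synopsis, DSMB row:** "The study will be evaluated for safety after the first 60 patients enrolled". This row contains the only numerical stopping rule in the protocol: freedom from MAE at 30 days, with a threshold of 78%, equivalent to a 22% event rate.
- **Section 6.4, Risk Mitigation:** "DSMB will meet at completion of the first 30 patients and at 60 patients to analyze procedural and follow up events". It continues: "Recommendations will be made to continue or stop the study based on these 2 interim analysis".
- **Section 4.665, Data Safety Monitoring Board:** "The DSMB will convene when 30-day safety data are available for 100 randomized subjects". It then adds: "Subsequently, the DSMB will review the data at time intervals per their discretion".

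On the design, section 4.1 states: "This is a prospective, multicenter (up to 14 sites), single arm study". The synopsis, the purpose statement in section 1.0 and section 4.47 (Blinding) agree that there is one arm.

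The list of changes at the end of the document does not touch DSMB timing, so all three passages are current text. No order of precedence between them is stated.

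**The concern.** A DSMB member would look first in section 4.665, which mentions no meeting before 100 subjects and places all other reviews after that one. A board that follows it would hold neither the 30-patient nor the 60-patient look, and the stopping rule attached to the 60-patient look would not be applied when the synopsis says it should be.

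This matters because section 1.0 (Intended Use) calls the use of the device in stents off label and investigational, and section 6.3 says its risks in in-stent restenosis have not been defined in a large trial. Section 6.4 offers the early looks as risk mitigation.

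There are two further defects. The 4.665 trigger counts randomized subjects, and this study has none. The triggers also differ in kind: patients enrolled (synopsis), completion of patients (6.4), and availability of 30-day data (4.665). The stopping rule needs 30-day outcomes, so the date on which it can be applied depends on which kind is meant.

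**Working it through.** The trigger is a stated rule and not a derived figure, so there is no calculation of the plan's to reproduce. The check sets the passages side by side and then sizes the gap.

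**Side by side**

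| Source | Looks | Trigger | Criterion given |
|---|---|---|---|
| Synopsis | 60 | enrolled | 78% freedom from 30-day MAE |
| Section 6.4 | 30 and 60 | completion of 30; at 60 patients | none stated; continue/stop recommendation |
| Section 4.665 | 100, then at discretion | 30-day data available, randomized subjects | none stated |

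The synopsis and 6.4 share the 60-patient look. The synopsis is silent on the 30-patient look. Neither contains a 100-patient look, and 6.4 counts exactly two interim analyses.

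**Timing by patient count.** Inputs: 140 planned (section 1.0, Number of Sites and Subjects); minimum 134 (section 5.12).

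- 30/140 = 21.4%; 30/134 = 22.4%
- 60/140 = 42.9%; 60/134 = 44.8%
- 100/140 = 71.4%; 100/134 = 74.6%
- Gap between the 60-patient look and the 4.665 look: 100 − 60 = 40 patients
- Left to enrol after 100: 140 − 100 = 40, or 134 − 100 = 34

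The 71.4% is a floor, because 4.665 waits for 30-day data while enrolment may continue.

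**Allowing for the 30-day lag (assumption-based).** The protocol gives no accrual rate. Section 1.0 says: "The estimated duration of the study is approximately two years from the time of first subject enrollment", counted to the last required visit. Assume this is 730 days, with the last 1-year visit at 320 to 410 days (window in Table 1), uniform accrual and no pause in enrolment. The 30-day visit window is 30 to 45 days.

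- Accrual period: 730 − 410 = 320 days to 730 − 320 = 410 days
- Rate: 140/410 = 0.3415 to 140/320 = 0.4375 per day
- Enrolled during the lag: 0.3415 × 30 = 10.2 to 0.4375 × 45 = 19.7
- Enrolled when 100 have 30-day data: 110.2/140 = 78.7% to 119.7/140 = 85.5%
- Enrolled when 60 have 30-day data: 70.2/140 = 50.2% to 79.7/140 = 56.9%

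The total duration is only approximate. Allowing 90 days either way gives accrual over 230 to 500 days. The first range then widens to 100 + (140/500) × 30 = 108.4 (77%) to 100 + (140/230) × 45 = 127.4 (91%).

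**What the missed look could detect.** At 60 patients the 22% event level is 0.22 × 60 = 13.2, so it is crossed at 14 events. If the true 30-day MAE rate were 30% (an illustrative assumption), the binomial probability of 14 or more events in 60 is 0.90. The look that 4.665 would bypass is therefore informative.

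**The case against.** The strongest counter-argument is that the schedules are cumulative: 30, 60, then 100, then at discretion. Section 4.665 does not say first or only, so no sentence is strictly violated. On this view, two passages already commit to the 60-patient look, and 4.665 is simply the outlier. Appendix A mentions an earlier 2:1 ratio, which may explain the reference to randomized subjects, although the documents do not say so.

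That the first meeting is at 100 is indeed an inference. It is still the natural reading, because the dedicated DSMB section names no earlier meeting and puts everything else after that one. Even the cumulative reading leaves a third look that the synopsis and 6.4 omit, and a trigger that cannot be met as worded. The passages need reconciling either way.

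Some of the other objections do stand:

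- The synopsis wording can be read as waiting for 30-day data, since its rule is on 30-day MAE. The difference in trigger is then an ambiguity to settle, not a flat contradiction.
- An early look at 30 patients can rest on judgement, so the lack of a numerical criterion there is not in itself an error.
- The lag projections rest on assumed accrual. The 40-patient gap does not.
- Clinical Events Committee review (sections 4.664 and 6.4) and 24-hour SAE reporting (section 4.657) continue throughout and limit the consequence. Neither is described as applying the 78% rule.
- Sample size, power and the primary analysis are unaffected.

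**Conclusion.** The concern holds. Section 4.665 cannot be followed as written together with the synopsis and section 6.4, and its reference to randomized subjects is wrong for this design. If it is followed with enrolled subjects substituted, the first review comes 40 patients after the look that carries the stopping rule, at no less than 71% of planned enrolment against 43%. Those figures need no assumption beyond the planned 140. Under the stated accrual assumptions, 79% to 85% would already be enrolled at the 4.665 trigger, leaving about 20 to 30 patients whom a stopping recommendation could still protect. The 60-patient look, if it also waited for 30-day data, would come at 50% to 57%.

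The documents do not show which schedule is intended. Because the conflict decides whether the only numerical safety rule is applied on time, it must be corrected.

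**What to change.** Reconcile the synopsis DSMB row, section 4.665 and section 6.4 so that all three give the same review schedule. The sponsor and DSMB should choose it. In the same edit:

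- Define one trigger for every look: either a number enrolled or a number with 30-day data available.
- In 4.665, replace randomized with enrolled.
- State at which look or looks the 78% rule applies.

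As an optional clarification, say that the rule counts the full 30-day composite, including TLR other than bailout stenting. The synopsis already defines 30-day MAE this way, but its 20% + 2% illustration does not itemise that component.

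The cost is wording in three passages, with no added patients, procedures or data collection.

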#### 4.666 CASE REPORT FORMS

Electronic case report forms (eCRFs) and paper CRF will be used to collect study data. The eCRFs will be reviewed and signed by the Principal Investigator attesting to their accuracy. All appropriate sections of the CRFs must be completed.

The Sponsor will use the study data for statistical and tracking purposes and will treat the information as confidential.

### **5.0 STATISTICAL METHODS**

#### 5.1 SAMPLE SIZE

#### 5.11 Meta-analysis of PTA control arms from randomized trials

Please refer to Appendix A at end of protocol

#### 5.12 Assumptions:

TLR with bailout stenting from historic control from meta-analysis:37.9%TLR with bailout stenting from Jetstream ISR feasibility study:20.7%Power 80%Alpha 0.05

We are planning a study of independent cases and controls with 1 control(s) per case. Prior data indicate that the failure rate among controls is 0.38. If the true failure rate for experimental subjects is 0.21, we will need to study 112 experimental subjects and 112 control subjects to be able to reject the null hypothesis that the failure rates for experimental and control subjects are equal with probability (power) 0.8 (meta-analysis from published randomized trials provides data on 182 controls). The Type I error probability associated with this test of this null hypothesis is 0.05. We will use an uncorrected chi-squared statistic to evaluate this null hypothesis. Assumingly a loss of 20% of patients on follow-up a minimum of 134 patients will be enrolled.

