### 5.25 ANALYSIS OF OUTCOMES

We hypothesize that JetStream atherectomy is superior to plain old balloon angioplasty in treating femoropopliteal in-stent restenosis in regards to the primary effectiveness endpoint of target lesion revascularization at 6 months with bailout stenting considered as a TLR. The Null Hypothesis assumes that the active control (JetStream) and the historic control of TLR (derived from the meta-analysis) have the same TLR at 6 months by intention to treat analysis. We calculated that if TLR is 0.38 for balloon angioplasty and 0.21 for JetStream, we need a total of 112 experimental subject and 112 control to reject the null hypothesis with a power of 0.8 and alpha of 0.05. The meta-analysis has provided data on TLR for balloon angioplasty in more than 112 controls. To account for patient loss to follow up we plan to enroll a maximum number of 140 patients in this study

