#### New Statistical analysis for Jet-ISR

TLR with bailout stenting from historic control from meta-analysis:37.9%TLR with bailout stenting from Jetstream ISR feasibility study:20.7%(2 bailout stent for suboptimal results + 4 TLR at 6 months/29 limbs)20.7%Power 80%Alpha 0.025

If one assumes a 1:1 ratio of actual treatment: control (instead of the original 2:1)

We are planning a study of independent cases and controls with 1 control(s) per case. Prior data indicate that the failure rate among controls is 0.38. If the true failure rate for experimental subjects is 0.21, we will need to study 112 experimental subjects and 112 control subjects to be able to reject the null hypothesis that the failure rates for experimental and control subjects are equal with probability (power) 0.8 (meta-analysis provides 182 controls which is more than needed for this analysis). The Type I error probability associated with this test of this null hypothesis is 0.05. We will use an uncorrected chi-squared statistic to evaluate this null hypothesis. Assumingly a loss of 20% of patients on follow-up a minimum of 134 patients will be enrolled.

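### The stated 80% power is for a 112 v 112 design, but this single-arm study is compared with 69/182 existing controls; against 182 controls, power is about 87.5%

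*Combined protocol and SAP*

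**What the plan says.** The synopsis, section 5.12 and Appendix A (New Statistical analysis for Jet-ISR) carry the same sample-size paragraph. It opens "We are planning a study of independent cases and controls with 1 control(s) per case". It continues: "Prior data indicate that the failure rate among controls is 0.38", and "If the true failure rate for experimental subjects is 0.21, we will need to study 112 experimental subjects and 112 control subjects". The stated power is 0.8. On error rate and test it says "The Type I error probability associated with this test of this null hypothesis is 0.05" and "We will use an uncorrected chi-squared statistic to evaluate this null hypothesis". Sidedness is not given. The assumptions line at the head of the Appendix A block lists alpha as 0.025, while the paragraph beneath it says 0.05.

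The synopsis and section 4.1 describe a single-arm study, and the synopsis names historic meta-analysis data as the comparator. Appendix A (Estimated Counts of TLR with Bailout Stenting at 6-Months) gives that comparator as 69/182, or 37.9%.

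On how the 182 relate to the required 112, the synopsis and 5.12 note in the sample-size sentence itself that 182 controls are available. Appendix A says "meta-analysis provides 182 controls which is more than needed for this analysis". Section 5.25, which sets out the analysis, says only "The meta-analysis has provided data on TLR for balloon angioplasty in more than 112 controls".

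Minimum enrolment is 134, allowing for 20% loss; the maximum is 140.

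**The concern.** A power statement should describe the comparison that will be made. Here it describes equal groups of 112, both to be sampled. No control group will be recruited, and the pooled control result already exists with a different denominator. A reader who takes the 80% at face value gets the wrong operating characteristics for the primary test, and also the wrong idea of how many JetStream patients that power requires.

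The second issue is the test itself. The plan names the statistic but does not state which control count goes into it. The remarks that there are more controls than needed leave a 112-control version conceivable, although no rule or patient-level source for choosing 112 of the 182 is offered. The control count moves the significance boundary, and section 4.47 records that the study cannot be blinded. The count should therefore be in writing before the JetStream result is known.

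**Working it through.** **Inputs.** Control rate 0.38, JetStream rate 0.21, alpha 0.05 and uncorrected chi-squared (synopsis, 5.12); control data 69/182 (Appendix A); minimum enrolment 134 with 20% loss (5.12). Assumption: the test is two-sided. This reproduces the plan's 112; one-sided 0.05 would give 88 per group, and two-sided 0.025 would give 136.

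**Formula.** With n1 JetStream patients and n2 controls:

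- pooled rate p̄ = (0.21·n1 + 0.38·n2)/(n1 + n2)
- s0 = √[p̄(1 − p̄)(1/n1 + 1/n2)]
- s1 = √[0.21·0.79/n1 + 0.38·0.62/n2]
- power = Φ[(0.17 − 1.96·s0)/s1]

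**Step 1: the plan's own figure.** For n1 = n2 = 112, p̄ = 0.295, s0 = 0.0609 and s1 = 0.0599. Power = Φ(0.844) = 80.1%. The stated 112 and 80% reproduce.

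**Step 2: the same test against 182 controls, treated as a sample.**

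| Evaluable JetStream | Controls | s0 | s1 | Power |
|---|---|---|---|---|
| 112 | 112 | 0.0609 | 0.0599 | 80.1% |
| 112 | 182 | 0.0558 | 0.0527 | 87.5% |
| 107 (134 × 0.8 = 107.2) | 182 | 0.0567 | 0.0533 | 86.5% |
| 84 | 182 | 0.0619 | 0.0572 | 80.3% |

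Exact enumeration for 112 v 182 gives 87.7%. The smallest JetStream group reaching 80% is 84.

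**Step 3: does the control count change the verdict?** A control scaled to 112 would be 0.379 × 112 = 42.4 or 0.38 × 112 = 42.6 events, so 42 or 43. These two counts are constructed here for the check and do not appear in the plan. The statistic is χ² = N(ad − bc)² divided by the product of the four margins.

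- 30/112 v 69/182: 294 × (30·113 − 82·69)² / (112·182·99·195) = 3.843, p = 0.04995.
- 30/112 v 42/112: 224 × (30·70 − 82·42)² / (112·112·72·152) = 2.947, p = 0.086.
- 30/112 v 43/112: 224 × (30·69 − 82·43)² / (112·112·73·151) = 3.434, p = 0.064.
- 29/112: p = 0.034 v 69/182, 0.062 v 42/112 and 0.045 v 43/112.

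At 30 events the verdict differs under either rounding. At 29 it differs only if the scaled control is rounded down to 42.

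**Step 4: control held fixed at 69/182.** Success then means at most 30 events in 112. With a true JetStream rate of 0.21, P(X ≤ 30) = 94.4%.

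**Step 5: cut-offs against 69/182 at other sizes.** The largest significant counts are 28/107, 30/112, 36/134 and 38/140.

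**The case against.** The best defence is that nothing is miscalculated. The plan states a requirement of 112 and 112, discloses 182 available controls beside it, and calls that more than needed. Extra controls can only raise power, so 80% is a floor that the design meets. All of this stands, and it rules out two readings: that the 80% is an arithmetic error, and that the trial is too small.

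A reader might also infer that the control count has been left for choice after the data are in. The documents do not support that. Section 5.25 defines the null hypothesis against the historic control from the meta-analysis, whose only pooled result is 69/182. No section proposes drawing 112 of the 182. What is missing is one explicit sentence.

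The boundary example is narrow. It needs exactly 112 evaluable patients, and at a true rate of 0.21 the chance of exactly 30 events is about 2.9%. It is also fragile, because the counts in Appendix A are labelled as estimated: with 68 rather than 69 control events, χ² = 294 × (30·114 − 82·68)² / (112·182·98·196) = 3.490, and p becomes 0.062. That limits the weight of the example but does not remove the need to name the control count.

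Finally, one might argue that the true power is 94%, with a one-sided false-positive rate near 0.9% (P(X ≤ 30) at a true rate of 37.9%). Both figures treat 37.9% as known without error. They ignore sampling error in 182 patients, and control rates in Appendix A that run from 26.0% to 48.2% across the three trials. Neither should be presented as the trial's operating characteristic.

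**Conclusion.** The point holds as a mismatch between the power statement and the design, in the conservative direction. The plan's 80% is correct for 112 v 112. For the comparison that the single-arm design makes, it understates power by about 7 points at 112 evaluable patients (87.5% against 80.1%), and it overstates the JetStream patients needed for 80% by 28 (112 against 84). These figures assume true rates of 0.38 and 0.21, a two-sided 0.05 test, and the 182 controls behaving as one random sample, as the plan itself treats them. If alpha were two-sided 0.025, power at 112 v 182 would be 80.3%, so the two alphas in Appendix A need to be reconciled.

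The control count for the test is implied but not stated, and at 30/112 events it decides significance. This is worth correcting before analysis. It is not a reason to change enrolment or to doubt that the trial is large enough on its own assumptions.

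**What to change.** In the synopsis, 5.12, 5.25 and Appendix A:

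1. Replace the one-control-per-case wording with a comparison of JetStream patients against all 182 balloon-angioplasty controls (69 events), by two-sided uncorrected chi-squared at one stated alpha. Reconcile the 0.05 with the 0.025 in Appendix A.
2. Restate power as about 87–88% at 112 evaluable patients (86.5% at 107), noting that the controls are treated as a sample. These figures are for two-sided 0.05.
3. If power conditional on a fixed 69/182 is shown (about 94%), give it only as a secondary figure, with the caveat that it ignores uncertainty and between-trial variation in the control rate.
4. State the success rule as the test itself, applied to the actual evaluable number. Counts such as 28/107, 30/112, 36/134 and 38/140 may be added as illustrations for alpha 0.05, not as the rule.

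The cost is an amendment to the wording. Enrolment of 134 to 140 and all trial procedures stay as they are.

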#### NUMBER OF SITES AND SUBJECTS

One hundred and 40 patients (140) subjects are planned for enrollment into this prospective registry at up to 14 study sites in the United States.

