### 4.2 PRIMARY OUTCOME

### Effectiveness

**Target Lesion Revascularization (TLR) at 6 months**: TLR is defined as retreatment of the index lesion (extended 1 cm proximal and distal to the lesion) at 6 months. For the primary endpoint, intra-procedural bail out stenting of the index lesion is considered meeting a TLR endpoint. (Intention to treat Analysis analysis)

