### 5.2 DATA ANALYSIS PLAN

#### **5.23** GENERAL PRINCIPLES

All statistical analyses will be performed using a widely accepted statistical or graphical software. An intention to treat analysis will be carried on with bailout stenting as TLR and without bail out stenting as TLR. Also analysis will be done by actual treatment. A maximum of 140 patients will be enrolled.

Descriptive statistics will be used to present the data and to summarize the results. Discrete variables will be presented using frequency distributions and cross tabulations. Continuous variables will be summarized by presenting the number of observations (N), mean, standard deviation, median, minimum, and maximum values.

For AE reporting, the primary analysis will be based on subject counts. A subject with more than one event will be counted only once toward the event rate based on the total number of subjects with AEs. An event rate based on event counts will also be presented. For example, if a subject experiences one major unplanned amputation of the treated limb and two clinically-driven TLRs within 30 days, the subject will be counted once in the rate of total subjects with a 30-day MAE; the same subject will be counted once in the individual event category of "Major Unplanned Amputation of the Treated Limb" and twice in the "Clinically-Driven TLR" category.

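### The enrolment floor of 134 does not cover the 20% loss it is meant to cover: it leaves about 107 evaluable patients, not 112 (small effect, since 140 are already planned)

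*Combined protocol and SAP*

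**What the plan says.** Section 5.12 sets the control failure rate at 0.38 ("Prior data indicate that the failure rate among controls is 0.38") and the Jetstream rate at 0.21. With 80% power, a type I error of 0.05 and an uncorrected chi-squared test, it arrives at 112 treated patients and 112 controls. It then allows for loss: "Assumingly a loss of 20% of patients on follow-up a minimum of 134 patients will be enrolled". The same sentence stands in the synopsis (statistical assumption and analysis) and in Appendix A (New Statistical analysis for Jet-ISR).

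Other sections give 140:

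- Section 1.0, Number of Sites and Subjects: "One hundred and 40 patients (140) subjects are planned for enrollment into this prospective registry".
- Section 5.23: "A maximum of 140 patients will be enrolled".
- Section 5.25: "To account for patient loss to follow up we plan to enroll a maximum number of 140 patients in this study".

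Appendix A lists an alpha of 0.025 among its assumptions. Its text for the same calculation then says: "The Type I error probability associated with this test of this null hypothesis is 0.05". It also refers to a 1:1 ratio "instead of the original 2:1".

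**The concern.** The sentence gives the loss as a share of patients and the 134 as the number enrolled, so 134 should still yield 112 after 20% are removed. It does not. It comes from adding 20% to 112, whereas the calculation should divide 112 by the 80% who remain.

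A minimum of 134 and a maximum of 140 do not contradict each other. The fault is that the floor does not do what its own sentence claims. Two numbers are offered as the allowance for loss, 134 in Section 5.12 and 140 in Section 5.25, and only the second is sufficient. A sponsor who stopped at the floor and lost the anticipated 20% would have followed the protocol and still missed its evaluable target.

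**Working it through.** **Inputs.** From Section 5.12: failure rates 0.38 (control) and 0.21 (Jetstream), power 0.80, type I error 0.05, uncorrected chi-squared test, 1:1 ratio, 20% loss, minimum 134, and 182 historical controls available. From Sections 1.0, 5.23 and 5.25: 140 planned, and 140 as the maximum. Sidedness is not stated; I take two-sided because it reproduces the plan's figure.

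**1. The plan's 112.** The mean rate is (0.38 + 0.21)/2 = 0.295 and the difference is 0.17.

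n per group = [1.96 × √(2 × 0.295 × 0.705) + 0.8416 × √(0.21 × 0.79 + 0.38 × 0.62)]² / 0.17² = 111.78, so 112. The plan's figure is reproduced.

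**2. The plan's 134.** 112 × 1.2 = 134.4, which gives 134 when rounded down. The calculation that matches the sentence is 112/(1 − 0.20) = 140.

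**3. What each number delivers.**

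| Enrolled | Evaluable after 20% loss | Largest loss that still leaves 112 |
|---|---|---|
| 134 | 134 × 0.80 = 107.2 | 1 − 112/134 = 16.4% |
| 140 | 140 × 0.80 = 112.0 | 1 − 112/140 = 20.0% |

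The shortfall at 134 is 112 − 107.2 = 4.8 patients.

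**4. Cost in power.** Historical controls do not shrink when treated patients are lost, so only the treated group is reduced. Pooled-variance z test, 0.21 v 0.38, two-sided 0.05, controls treated as a simple binomial sample:

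| Evaluable treated | v 112 controls | v 182 controls |
|---|---|---|
| 112 | 80.1% | 87.5% |
| 107 | 79.1% | 86.5% |

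Against 182 controls, 84 evaluable patients already give 80.3% power. On that basis 134 enrolled would tolerate 1 − 84/134 = 37.3% loss.

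**5. Lost patients with a known outcome.** Section 4.2 says: "For the primary endpoint, intra-procedural bail out stenting of the index lesion is considered meeting a TLR endpoint". A patient with a bailout stent therefore has a known event on the day of the procedure, even if lost later. Of the 134 × 0.20 = 26.8 lost, 4.8 (4.8/26.8 = 18%) would need a known outcome to bring the count back to 112. The documents do not say how many would.

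**6. Alpha in Appendix A.** The same formula gives 112 at two-sided 0.05 and also at one-sided 0.025, which has the same critical value. At two-sided 0.025 it gives 135.5, so 136 per group, and 112 v 112 would have 71.2% power. The printed 112 therefore does not fit a two-sided 0.025.

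**The case against.** The strongest reply is that the right number is already in the protocol. Section 1.0 plans 140, Section 5.25 ties 140 to loss to follow-up, and 140 × 0.80 is exactly 112. Nothing says enrolment is meant to stop at 134. This limits the consequence but does not rescue the sentence, because 140 is a ceiling in Sections 5.23 and 5.25 and 134 is the stated floor.

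A second reply is that the gap depends on rounding. The listed assumptions are 37.9% and 20.7%, and those rates need 108.7, so 109 per group. The shortfall is then about 2 patients (109 − 107.2 = 1.8), and 107 v 112 controls has 80.2% power, so the 80% target is met. This is correct and worth knowing. However, the protocol's own requirement is 112, and even 109 would need 109/0.80 = 136.25 enrolled, more than 134. The cost is still about one point of power (80.2% v 81.2% at 112 v 112).

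A third is that the primary analysis is by intention to treat and some lost patients will have a recorded event, so 107 is conditional. That stands as a caveat. Section 5.12 makes no such allowance when it derives 134.

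On alpha, 0.025 may simply be the one-sided equivalent of two-sided 0.05, which would be harmless. The documents do not settle it.

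**Conclusion.** The point holds, as a minor arithmetic error repeated in three places. The base sample size is sound; only the loss adjustment is wrong. The size of the error rests on the protocol's rounded rates, a two-sided 0.05 test, a full 20% loss, and no known primary outcome among those lost. The power figures also treat the historical controls as an ordinary independent sample, as the plan does. Enrolling the planned 140 removes the shortfall, so the practical risk is low.

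The alpha discrepancy is secondary. The synopsis, Section 5.12 and the text of Appendix A all state 0.05, so the printed figures stand. It matters only if a two-sided 0.025 was intended.

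**What to change.** In the synopsis, Section 5.12 and Appendix A, do one of the following:

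- replace the minimum of 134 with 140, showing 112/0.80, and note that this equals the stated maximum and leaves no reserve; or
- keep 134 and state that it preserves 112 evaluable patients only up to about 16% loss.

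In Appendix A, reconcile the listed alpha with the text and state the level with its sidedness. Two-sided 0.05 fits the printed 112. Label the 0.025 as one-sided only if the sponsor confirms that this was meant.

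The cost is wording only: neither the test nor the planned 140 changes. The first option makes the six patients between 134 and 140 obligatory; the second avoids that.
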